Based on the clinical data available to date in the adult population, treatment with alirocumab has demonstrated a significant LDL-C lowering effect in a population of patients with non-FH or with heFH. The LDL-C lowering efficacy was associated with consistent decreases in Total-C, Apo B, non-HDL-C, a decrease in Lp(a), and a favorable trend for HDL-C and triglycerides. Maximum efficacy was observed as early as 4 weeks after the initial dose, and efficacy was well maintained up to 2 years.

Alirocumab administration to date in clinical trials has been associated with a favorable safety and tolerability profile.

Immunogenicity and systemic hypersensitivity are considered as identified risks.

Injection site reactions (including erythema/redness, itching, swelling, pain, tenderness), upper respiratory tract signs and symptoms (including mainly oropharyngeal pain, rhinorrhea, sneezing), pruritus, hypersensitivity, eczema nummular, urticaria, and hypersensitivity vasculitis are identified as adverse drug reactions (ADRs) for alirocumab. ADRs include AEs for which there is some basis to believe that there is a causal relationship between the drug and the occurrence of the AE.

Monitoring of these AEs will be continued in all studies conducted in adult and pediatric patients.

There was no safety signal observed with neurologic events, alanine aminotransferase (ALT) increase and hepatic disorders, adjudicated CV events, diabetes mellitus, skeletal-muscle related disorders and ophthalmologic disorders in the alirocumab-treated group overall, but more cataracts (2.6%) were noted in patients treated with alirocumab who achieved 2 consecutive LDL-C values <25 mg/dL compared to 0.8% of alirocumab-treated patients who did not achieve such low levels. Although limitation has to be consider with regard to this post-randomization comparison and there were no statistically significant differences in the incidence of cataracts in this subgroup of patients when compared to control groups, cataract in patients with very low LDL-C levels is considered as a potential risk and the Sponsor will continue to monitor this potential risk. There was no safety signal observed for neurocognitive disorders, however, the Sponsor will monitor this potential risk as an adverse event of special interest in this study.

An independent Data Monitoring Committee (DMC) dedicated to the pediatric clinical program conducted with alirocumab will meet periodically to review the safety data collected in this study.

This specific study is undertaken to demonstrate the safety and the reduction of LDL-C with alirocumab in the heFH pediatric population and to support appropriate dose selection for the Phase 3 study. Because of the rapid clinical progression of atherosclerotic disease in children and

adults with familial hypercholesterolemia pediatric guidelines recommend LDL-C lowering intervention starting with statins. However, not all patients can achieve target LDL-C reductions with currently available LMTs, and these pediatric patients represent a group with an identified unmet medical need that can be addressed by adding alirocumab to their LDL-C lowering therapies. Different doses according to BW categories (<50 kg and ≥ 50 kg) will be evaluated through, in the first step, through 3 sequential independent cohorts with treatment duration of 8 weeks, followed by 6 or 8-week post-treatment follow-up period. An additional cohort, Cohort 4, will evaluate further the Q4W dosing regimen over a treatment of 12 weeks.

5 STUDY OBJECTIVES

5.1 PRIMARY

The primary objective of the study is to evaluate the effect of alirocumab administered Q2W or Q4W on low-density lipoprotein cholesterol (LDL-C) levels after 8 weeks of treatment in heterozygous familial hypercholesterolemia (heFH) patients aged of 8 to 17 years, with LDL-C ≥ 130 mg/dL (3.37 mmol/L) on optimal stable daily dose of statin therapy \pm other lipid modifying therapies (LMTs) or a stable dose of non-statin LMTs in case of intolerance to statins, for at least 4 weeks prior to the screening period.

5.2 SECONDARY

- To evaluate the safety and tolerability of alirocumab.
- To evaluate the pharmacokinetics profile of alirocumab.
- To evaluate the effects of alirocumab on other lipid parameters (eg, Apolipoprotein B (Apo B), non-high density lipoprotein cholesterol (non-HDL-C), Total-Cholesterol (Total-C), high-density lipoprotein cholesterol (HDL-C), Lipoprotein (a) (Lp[a]), Triglycerides (TGs), Apolipoprotein A-1 (Apo A-1) levels after 8 weeks of treatment.
- To evaluate the development of anti- alirocumab antibodies.

6 STUDY DESIGN

6.1 DESCRIPTION OF THE PROTOCOL

This study is an open-label, dose-finding, sequential group, multi-national, multi-center study with repeated dose of subcutaneous (SC) alirocumab injections administered every 2 weeks (Q2W) or every 4 weeks (Q4W) in children and adolescents aged of 8 to 17 years with heFH having LDL-C ≥ 130 mg/dL (3.37 mmol/L). A sequential enrollment into the 4 separate and independent Cohorts 1 to 4, is applied. Patients should be treated with an optimal dose of statin with or without other LMT(s), or non-statin LMT(s) if statin intolerant, at stable daily dose(s) for at least 4 weeks. The optimal dose of statin is defined as the stable daily dose prescribed based on regional practice or local guidelines or is the stable daily dose that is maximally tolerated due to adverse effects on higher doses. For patients not receiving maximally tolerated dose of statin, statin intensification should be carefully considered prior to inclusion in this study in order to ensure that the addition of a non-statin LDL-C lowering therapy (ie, alirocumab) would be the next appropriate step in the management of the patient's hypercholesterolemia. The highest dose of statin should not exceed the maximum labeled dose of statin for pediatric patients as per the local prescribing information. Each independent cohort below will include 10 patients with no less than 4 patients in each BW category:

- Cohort 1 will receive 30 mg Q2W for body weight (BW) < 50 kg and 50 mg Q2W for BW ≥ 50 kg.
- Cohort 2 will receive 40 mg Q2W for BW < 50 kg and 75 mg Q2W for BW ≥ 50 kg.
- Cohort 3 will receive 75 mg Q4W for BW < 50 kg and 150 mg Q4W for BW ≥ 50 kg.
- Cohort 4 will receive 150 mg Q4W for BW < 50 kg and 300 mg Q4W for BW ≥ 50 kg.

For each cohort, the study consists of a main phase and an optional extension phase. The main phase is comprised of 3 periods; screening (including run-in, if applicable), open-label dose finding treatment, and follow-up only for Cohorts 1, 2, and 3, and 2 periods: screening (including run-in, if applicable) and open-label dose finding treatment for Cohort 4. These periods of the main phase are described as below.

MAIN PHASE:

Screening Period:

- The screening period will last up to 6 (+1) weeks, with patients to be enrolled as soon as all inclusion and no exclusion criteria are met.
 - Patients who consent to participate in the study, but who have not been on stable LMTs for at least 4 weeks or require statin intensification when initially seen, can participate in a run-in period until LMT dose(s) have been stable for 4 weeks, and be enrolled when eligibility is confirmed, including eligible LDL-C value obtained after stable LMT dosing has been maintained for at least 4 weeks. Stable LMT refers to patients receiving either stable optimal daily dose of statin \pm other LMT(s) or stable dose of non-statin LMT(s) if statin intolerance for at least 4 weeks prior to screening.

It is not authorized to select patients treated with statin *de novo*, to avoid unstable lipid modifying treatment (LMT) during the screening period.

- Patients suspected of having heFH but without confirmation (prior genetic testing results obtained or diagnosed clinically by Simon Broome criteria) will undergo genetic testing, once separate consent for heFH genotyping is signed, and can be enrolled when eligibility is confirmed. This genotyping will be mandatory for patients without either clinical diagnosis or without previous documented genotyping who consent to participate in the study.

This genotyping testing is offered optionally to others whose heFH diagnosis has already been confirmed (prior genetic testing results obtained or diagnosed clinically by Simon Broome criteria). If patients agree to perform this centralized genotyping and/or they agree to use a previous documented genotyping, they will be required to sign a separate genetic testing informed consent form (ICF) prior to collection of the DNA sample and/or request for previous genotyping results.

If the diagnosis of heFH to establish eligibility is based on clinical criteria or a documented previous genotyping, the results of this elective centralized genotyping will not impact their eligibility inclusion.

- The report of the heFH genotyping done as part of this study will provide an interpretation of the results. However, all patients should have their results reviewed with a genetics counselor or equivalent. Genetic testing performed will be limited to testing for heFH-associated genes only. All samples will be destroyed once testing is completed. No additional genetic testing and no long-term storage will be done for these samples.
- Special procedures, including procedures for collection, handling, storage and shipment of DNA specimens for genetic testing for heFH, are summarized in the genetic testing manual provided by the central lab performing heFH testing.

All patients who successfully screen for Cohort 1 and are not included in Cohort 1, due to the appropriate Cohort 1 weight group being fully enrolled, may participate to Cohort 2 but only after eligibility, including safety assessments, is reconfirmed. Patients who are successfully screened for Cohort 2 but are not enrolled, due to the appropriate Cohort 2 weight group being fully enrolled, may participate in Cohort 3 without the need to repeat the run-in/screening period if there is no more than 3 months between eligibility confirmation and inclusion. In such a circumstance, the run-in/screening period from Cohort 2 will substitute for the run-in/screening period for Cohort 3. If there is more than 3 months between initial screening and planned enrollment in Cohort 3, patient eligibility, including safety assessments, must be reconfirmed.

Safety and eligibility assessments noted above include all lab tests listed as exclusionary, based on specified results.

Patients should be instructed to follow a diet in accordance with the American Academy of Pediatrics (AAP) guidelines (1) or equivalent throughout the entire study (ie, both phases). The dietitian or site staff with appropriate training will review the patient's diet at the screening visit and periodically throughout the study.

Main Open-Label Dose Finding Treatment Period:

- An open-label dose finding treatment period of 8 weeks with alirocumab for Cohorts 1 to 3, and 12 weeks for Cohort 4. Four independent cohorts (Cohorts 1 to 4) will be administered SC alirocumab injections Q2W or Q4W in a sequential enrollment.
- The DMC will review data on a regular basis during the dose finding treatment period.
- After Cohort 1 completes the open-label dose finding treatment period, the DMC will continue to review the safety data and make a recommendation on dose escalation to Cohorts 2 and 3. Cohort 2 will initially begin enrollment. Once enrollment is completed for Cohort 2, then this will immediately be followed by enrollment into Cohort 3 (ie, sequential enrollment). Cohort 4 is an independent cohort with a separate enrollment.
- Cohorts 1 and 2 (Q2W): Alirocumab injections will be prepared from vials by the pharmacist (or equivalent). Detailed instructions on preparation of injections from vials will be provided in a separate document. Alirocumab injections will be administered at Weeks 0, 2, 4, and 6. The Weeks 0 and 4 alirocumab injections will be administered at the clinical site by the site staff. The Weeks 2 and 6 alirocumab injections will be administered at the clinical site by the site staff or at the patient's home by a health care professional, depending upon local arrangements and preferences of the investigator/patient.
- Cohort 3 (Q4W): Alirocumab injections will be prepared from vials by the pharmacist (or equivalent). Detailed instructions on preparation of injections from vials will be provided in a separate document. Alirocumab injections will be administered at Weeks 0 and 4 at the clinical site by the site staff.
- Cohort 4 (Q4W): Alirocumab injections will be administered with prefilled syringes. Alirocumab injections will be administered Week 0, Week 4, and Week 8 at the clinical site by site staff.
- The lipid results from specimens obtained during the open-label dose finding treatment period will be masked for the clinical site/Investigator and patients. No attempts should be made by the investigator or patient to routinely have the patient's lipid values independently evaluated after entry into the open-label dose finding treatment period and until the final follow-up visit for Cohort 1, Cohort 2, and Cohort 3, and entry into the OLE period for Cohort 4. The sponsor and the DMC will closely monitor the lipid results during the 8-week open-label dose finding treatment period. If any safety concerns are noted during this period, including very low LDL-C levels (ie, LDL-C <50 mg/dL [1.30 mmol/L] on one or more occasion), then appropriate action will be taken by the Sponsor in consultation with the DMC.

Follow-Up Period, only for Cohorts 1 to 3:

- A follow-up period (off treatment) of 6 (Cohort 3) or 8 weeks (Cohorts 1 and 2) after the end of open-label dose finding treatment period visit. For these 3 cohorts, the final follow-up visit corresponds to 10 weeks after the last alirocumab injection administered during the open-label dose finding treatment period, since the last injection for Cohorts 1 & 2 is Week 6 and for Cohort 3 it is Week 4.

The daily optimal dose of statin or of other LMT (if applicable) should be stable from screening through the end of the follow-up visit unless there is a safety concern, as per the Investigator's judgment.

Cohorts 1 to 3 will have a follow-up period before entry in the extension period.

Open-label extension treatment period:

At the end of the follow-up period of the main phase for Cohorts 1 to 3 and end of the 12 week open label dose-finding for Cohort 4, patients enrolled in all cohorts who successfully complete (provided they have not experienced AEs leading to permanent discontinuation during the main treatment period, or had significant protocol deviations, in the investigator's judgment) the main phase will be offered entry into an optional extension phase. The extension phase includes an open-label extension (OLE) period as follows:

- All doses/dose regimen administered during the open-label dose finding treatment period of the main phase are expected to be efficacious. Thus, the initial dose of alirocumab that will be administered Q2W or Q4W during the OLE period, will be a continuation of the same doses/dose regimen administered during the open-label dose finding treatment period of the main phase. However, once the final optimal doses for the phase 3 study are selected, then these final optimal doses from the Q2W or Q4W regimen will be administered to all patients during the OLE period, based on the patient's body weight at the time of the dose change. For Cohort 4, patients will remain on their initial regimen given the planned study end date of December 2018.
- For Cohorts 1 to 3, alirocumab injections may be prepared from vials by the pharmacist (or equivalent) or supplied as prefilled syringes (PFS) depending on availability and additional considerations:
 - If the PFS is available in the extension phase, then patients may either switch from alirocumab injections prepared from vials to PFS or directly initiate PFS (depending on patient's date of entry into the extension phase). After appropriate training, the parent/guardian or patient (if appropriate) will administer the PFS at home or another preferred location. In certain cases, alternative arrangements may be made for the administration of the PFS,
 - If the PFS is not available in the extension phase, then alirocumab injections prepared from vials will be administered at the clinical site (by the site staff) or at the patient's home or another preferred location contingent upon alternative arrangements being made for such an administration.
- All patients from all cohorts that participate in the DFI14223 study will have the opportunity to enroll in the pediatric phase 3 study provided that they meet the eligibility criteria. The alirocumab administrations during the OLE period will continue until at least 10 weeks (corresponding to the wash out period) before the initiation of the pediatric phase 3 study in the site where the patient is potentially participating or December 2018 at the latest.
- The lipid levels will be communicated to the investigator during the OLE period. The Investigator will be responsible, based on his/her own judgment related to the patients' LDL-C levels and the safety profile, to continue or discontinue alirocumab throughout the study. The daily dose of statin should be maintained; in particular any decreases in statin

dose are strongly discouraged, except in case of medical reason. The statin dose should not be decreased to adjust to the degree of LDL-C lowering; the Investigator has the option to discontinue alirocumab. Other LMT (if applicable) can be modified based on the Investigator's judgment throughout the study. Further recommendations for the management and monitoring of patients who achieve very low LDL-C levels (ie, LDL-C <50 mg/dL [1.30 mmol/L] on one or more occasion) are provided in [Section 10.6.3](#).

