
	
dose escalation to Cohorts 2 and 3. Cohort 2 will initially begin enrollment. Once enrollment is completed for Cohort 2, then this will immediately be followed by enrollment into Cohort 3 (ie, sequential enrollment). Cohort 4 is an independent cohort with a later start date.
 
• Cohorts 1 and 2 (Q2W): Alirocumab injections will be prepared from vials by the pharmacist (or equivalent). Alirocumab injections will be administered at Weeks 0, 2, 4, and 6. The Weeks 0 and 4 alirocumab injections will be administered at the clinical site by the site staff. The Weeks 2 and 6 alirocumab injections will be administered at the clinical site by the site staff or at the patient's home by a health care professional, depending upon local arrangements and preferences of the investigator/patient.• Cohort 3 (Q4W): Alirocumab injections will be prepared from vials by the pharmacist (or equivalent). Alirocumab injections will be administered at Weeks 0 and 4 at the clinical site by the site staff.• Cohort 4 (Q4W): Alirocumab injections will be administered with pre-filled syringes by the site staff. Alirocumab injections will be administered at Week 0, Week 4, and Week 8 at the clinical site by the site staff.• The lipid results from specimens obtained during the open-label dose finding treatment period will be masked for the clinical site/Investigator and patients. No attempts should be made by the investigator or patient to routinely have the patient's lipid values independently evaluated after entry into the open-label dose finding treatment period and until the final follow-up visit for Cohorts 1 to 3, and the entry into the OLE period for Cohort 4 
Follow-Up Period, only for Cohort 1 to Cohort 3:
 
• A follow-up period (off treatment) of 6 (Cohort 3) or 8 weeks (Cohorts 1 & 2) after the end of open-label dose finding treatment period visit. For the first 3 cohorts, the final follow-up visit corresponds to 10 weeks after the last alirocumab injection administered during the open-label dose finding treatment period, since the last injection for Cohorts 1 & 2 is Week 6 and for Cohort 3 it is Week 4. 
The daily optimal dose of statin therapy or of other LMT (if applicable) should be stable from screening through the end of the follow-up visit unless there is a safety concern, as per the Investigator's judgment.
 
At the end of the follow-up period of the main phase, patients enrolled in Cohorts 1-3 and who successfully completed the main phase will be offered entry into an optional extension phase.
 
For Cohort 4, patients who successfully completed the open-label dose-finding treatment period will be offered entry into an optional extension phase with latest end date of December 2018 or direct entry into the Phase 3 study, depending on the time of site initiation.

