The addition to the higher doses in the Q4W cohort with extended 12 week study duration (including 2 new visits at Week 10 and Week 12) for the open label dose-finding period will more appropriately ensure that steady state has been reached after 3 alirocumab injections (2 interdose intervals) in terms of PK and LDL-C and related parameter reduction efficacy. An intermediate visit between the dosing interval (Week 10) is specifically introduced to better document the PK and LDL-C data from the Q4W dosing regimen that is known to show some peak-trough variability over the 4-week dosing interval, ie, a peak in the decrease at the mid dosing interval time point and trough reduction in LDL-C at the end of dosing interval time period. Thus, extending the duration of a higher Q4W dosing regimen to 12 weeks (an additional 4 weeks) will secure more comprehensively data on the LDL-C related profile reduction potential of a Q4W dosing regimen for alirocumab.

Given the 12 week duration, only LDL-C and key related parameters (TC, non-HDL-C, and TG) will be measured at Week 10 and Week 12 to minimize blood collection. The post-treatment follow-up period is no longer needed based on the data collected from the previous 3 cohorts.

All patients in Cohort 4 will receive alirocumab at 150 mg Q4W for BW <50 mg/300 mg Q4W for BW \geq 50 kg using prefilled syringes.

Cohort 4, similar to the other cohorts, will include alirocumab administration during the open-label extension that will continue until approximately 10 weeks before the initiation of the pediatric phase 3 study or December 2018 at the latest. The patients, after a wash-out period of at least 10 weeks after the last injection of alirocumab, will have the opportunity to participate in the phase 3 study. Though Cohorts 1 to 3 will be switched to the optimal regimen selected for the phase 3 study, Cohort 4 will remain on their initial regimen given the planned study end date of December 2018.

Conclusion on the benefit risk assessment with alirocumab:

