10.6.2.2 Acute allergic injection reactions

Acute allergic injection reaction (which are considered under the category of general allergic drug reactions) is defined as any adverse event that occurs during or shortly after injection of the IMP (characterized by but not limited to hypotension, bronchoconstriction, urticaria, edema, angioedema, nausea, vomiting). Emergency equipment and medication for the treatment of these potential adverse effects (eg, antihistamines, bronchodilators, IV saline, corticosteroids, acetaminophen, and epinephrine) must be available for immediate use for the injections at the site visits.

Patients will be observed at the investigational site for at least 30 minutes following the injection that takes place at the inclusion visit. Patients should be treated symptomatically if any AEs are observed. Patients are to remain at the site until any acute injection reaction is assessed as stable, per the Investigator's discretion. General Allergic Reaction and/or Local Injection Site Reaction Complementary Form will have to be completed.

10.6.3 Recommendations for managing and monitoring patients with very low LDL-C levels (ie, LDL-C<50 mg/dL [1.30 mmol/L]) during the OLE period

If a patient achieves a very low LDL-C level (ie, LDL-C<50mg/dL [1.30 mmol/L] on one or more occasion) during the OLE period, then the Investigator will:

- Call the patient / parent as soon as possible to inquire about interval occurrence of AEs, particularly any AEs related to visual problems.
- Decide whether the patient should be requested to rapidly have an unscheduled site visit, or assessment could be done at the next scheduled visit.
- At the site visit, plan for the following, based on Investigator's medical judgment:
 - Assess the need to have blood drawn from the patient for a repeat lipid assessment in order to confirm the observation of very low LDL-C,
 - Assess the need for conducting clinical investigations, arranging specialist consultation(s) as needed, including with an eye specialist in case of visual problems, as needed, and any relevant additional work-up,

- Assess the need for alirocumab treatment temporary or permanent discontinuation, or continuation. Regardless of the action taken regarding alirocumab treatment, the patient should continue the study,

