11 STATISTICAL CONSIDERATIONS

11.1 DETERMINATION OF SAMPLE SIZE

No power sample size calculations were performed for the main phase. A sample size of 10 patients per cohort is empirical and based on the sample size of the Phase 1 studies (R727-CL-904 and R727-CL-1001) conducted in adults. No less than 4 patients with BW <50 kg and no less than 4 patients with BW \geq 50 kg will be enrolled in 4 independent cohorts (Cohort 1, Cohort 2, Cohort 3, and Cohort 4), which will allow the evaluation of the pharmacokinetics/pharmacodynamics (PK/PD) profile and safety of different alirocumab doses/dose regimen in each BW category and to compare with PK/PD profile and safety observed in adult patients.

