2.1.4.4 Vital signs variables

Vital Signs parameters include Weight, Heart Rate (HR), Systolic and Diastolic Blood Pressure (SBP and DBP) in sitting position and were to be measured during:

- Screening at Visit 1 (up to Week -6),
- The OLDFI period at Visit 2 (Week 0), Visit 4 (Week 4), Visit 6 (Week 8) for Cohorts 1 to 4 or early termination (for Cohorts 1 to 3), and Visit 8 (follow-up visit for Cohorts 1 to 3, Week 14 for Cohort 3 or Week 16 for Cohorts 1& 2, and Week 12 or early termination for Cohort 4,

- The OLE period at Visit 8 (Week 16 for Cohorts 1& 2 or Week 14 for Cohort 3, or Week 12 for Cohort 4), Visit 12 (Week 40 for Cohorts 1& 2 or Week 38 for Cohort 3 or Week 36 for Cohort 4), Visit 13 (Week 48/ end of OLE period for Cohort 4), Visits 14, 16, 18 (every 24 weeks for Cohorts 1 to 3) and Visit 20 (Week 130/ end of OLE period for Cohorts 1 to 3 or early termination during OLE period for all cohorts).

2.1.4.5 *Electrocardiogram variables*

Not Applicable.

2.1.4.6 *Tanner stages measurement*

Tanner stages measurement include assessments of boys—development of external genitalia, girls—breast development, boys/girls—pubic hair, performed if possible by the same investigator/designee trained to assess pubertal development, during:

- Screening at Visit 1 (up to Week -6)
- The OLDFI period at Visit 8 (follow-up visit for Cohorts 1 to 3, Week 14 for Cohort 3 or Week 16 for Cohorts 1& 2) or Week 12 or early termination for Cohort 4,
- The OLE period at Visit 8 (Week 16 for Cohorts 1& 2 or Week 14 for Cohort 3 or Week 12 or early termination for Cohort 4), Visit 12 (Week 40 for Cohorts 1& 2 or Week 38 for Cohort 3 or Week 36 for Cohort 4), Visit 13 (Week 48/ end of OLE period for Cohort 4), Visits 14, 16, 18 (every 24 weeks) and Visit 20 (Week 130/ end of OLE period for Cohorts 1 to 3 or early termination during OLE period for all cohorts).

2.1.4.7 *Other endpoints*

Other endpoints listed below are defined using same definitions and rules as for calculated LDL-C, when applicable (see [Section 2.1.3](#)) and include:

- The proportion of patients with two consecutive results, spaced out by at least 21 days, of LDL-C <50 mg/dL (<1.30 mmol/L) and (calculated LDL-C <25 mg/dL ie, <0.65 mmol/L) respectively during OLDFI period or the OLDFI/OLE combined period
- The time to the first LDL-C <50 mg/dL (respectively, calculated LDL-C <25 mg/dL) for these patients within the relevant analysis period specified above.

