If applicable, similar summaries of TEAEs as those described above will be also provided on the safety subgroup population of patients with two consecutive results of calculated LDL-C <50 mg/dL (respectively calculated LDL-C <25 mg/dL) (as defined in [Section 2.1.4.7](#)). Only TEAE for which it will be confirmed or unclear that they occurred, worsened or became serious the day or after the first level of LDL-C <50 mg/dL (or LDL-C <25 mg/dL) will be considered. In case very few cases are observed, individual data listings of TEAEs will be provided on this subgroup of patients instead.

In addition, for the OLDFI/OLE combined period, the following summary tables will be provided:

- The event rate per patient year (the number of patients with an event in question divided by total patient-years) will be provided for all TEAEs by SOC and PT. For a patient with event, patient year is censored at time of first event; for patient without event, it corresponds to length of OLDFI/OLE combined TEAE period
- Kaplan-Meier curves will be provided, when appropriate, for time from first dose of OLDFI IMP to the first occurrence of selected TEAEs. Patients without any event will be censored at the end of the OLDFI/OLE combined TEAE period.

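### Cohort 4 runs 12 weeks, but the text assigning sponsor action on masked very low LDL-C says 8 weeks, and the SAP's 21-day spacing rule does not fit its Week 8, 10 and 12 samples

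*Protocol*

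**What the plan says.** **Duration and masking.** Protocol 6.1 provides "An open-label dose finding treatment period of 8 weeks with alirocumab for Cohorts 1 to 3, and 12 weeks for Cohort 4". Cohort 4 is injected at Weeks 0, 4 and 8. The synopsis asks that lipids not be checked independently "until the final follow-up visit for Cohorts 1 to 3, and the entry into the OLE period for Cohort 4", and Protocol 8.3.2 withholds main-phase lipid values from the sites.

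**Surveillance while masked.** Protocol 6.1 then states: "The sponsor and the DMC will closely monitor the lipid results during the 8-week open-label dose finding treatment period". The next sentence makes the sponsor, with the DMC, responsible for acting on safety concerns in that period, and names LDL-C below 50 mg/dL. A single value is enough. Section 10.6.3, which begins "If a patient achieves a very low LDL-C level", is limited to the extension (OLE).

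**SAP endpoint.** Section 2.1.4.7 defines "The proportion of patients with two consecutive results, spaced out by at least 21 days, of LDL-C <50 mg/dL", with a parallel rule at 25 mg/dL, for the dose-finding period (OLDFI) and for OLDFI and OLE combined. Time to the first low value is analysed only for patients who meet the rule. Section 2.4.5.1 summarises TEAEs in "the safety subgroup population of patients with two consecutive results of calculated LDL-C <50 mg/dL", by reference to the same definition.

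**Schedule.** Cohort 4 lipids are drawn after baseline at Weeks 4, 8, 10 and 12. Protocol 4 explains that Week 10 was added because four-weekly dosing shows "a peak in the decrease at the mid dosing interval time point".

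**The concern.** Both rules fit an 8-week period with post-baseline lipids at Weeks 4 and 8. Cohort 4 added a third injection, four more masked weeks and two more lipid samples, and neither rule was visibly adapted.

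- **Protocol.** The Week 10 value is the one chosen to show the deepest fall. It is masked to the site and lies outside the period named in the only text that assigns sponsor action on very low LDL-C under masking.
- **SAP.** The Week 10 sample splits the 28-day interval between Weeks 8 and 12 into two 14-day intervals. Under a literal reading, an additional low value can stop a child from being counted.

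Protocol 4 treats cataract with very low LDL-C as a potential risk and describes it through patients with two consecutive values below 25 mg/dL. The subgroup is therefore meant to be informative, and Cohort 4 has the highest four-weekly doses in the study.

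**Working it through.** **A. Which text covers a masked low value in Cohort 4?**

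| Text | Names very low LDL-C? | Period |
|---|---|---|
| Protocol 6.1, monitoring and action sentences | Yes | 8 weeks |
| Protocol 6.1, regular DMC review | No | Dose-finding period (12 weeks for Cohort 4) |
| Protocol 6.4, DMC safety review | No | Periodic, Cohort 4 included |
| Protocol 8.3.4, unblinded lipids to the DMC | No | No limit stated |
| Protocol 10.6.3, investigator steps | Yes | OLE only |

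Weeks 4 and 8 fall under the first row. Week 10 falls under no row that names very low LDL-C. Week 12 is also the first OLE visit for children who enter the OLE (Protocol 1.4.2, footnote a), so 10.6.3 can apply to them. For children who do not enter, Week 12 is in the same position as Week 10.

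**B. Does the 21-day spacing fit the schedule?**

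*Inputs.* Target days come from SAP Table 3. Visit windows come from Protocol 1.3.2: ±3 days at Weeks 4 and 8, ±7 days at Weeks 10 and 12. The 21-day spacing comes from SAP 2.1.4.7.

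*Plan's own figures.* Target day = 7 × week + 1 gives 29, 57, 71 and 85 for Weeks 4, 8, 10 and 12, as in Table 3.

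*Gaps.* Nominal gap = difference in target days. The range adds and subtracts both windows.

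| Pair | Nominal gap (days) | Range (days) | Combinations with gap ≥21 |
|---|---|---|---|
| Week 4-8 | 28 | 22 to 34 | 49/49 |
| Week 8-10 | 14 | 4 to 24 | 10/105 (9.5%) |
| Week 10-12 | 14 | 0 to 28 | 36/225 (16%) |
| Week 8-12 (not adjacent) | 28 | 18 to 38 | 99/105 (94%) |

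Let a, b and c be the deviations in days at Weeks 8, 10 and 12.

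- Week 8-10 needs b − a ≥ 7. For b = 7, 6, 5, 4 this allows 4 + 3 + 2 + 1 = 10 of 7 × 15 = 105 combinations.
- Week 10-12 needs c − b ≥ 7, which allows 8 + 7 + … + 1 = 36 of 15 × 15 = 225.
- Week 8-12 fails only if c − a ≤ −8, which is 3 + 2 + 1 = 6 of 105, leaving 99.
- The two adjacent conditions cannot hold together: the first needs b ≥ 4, the second b ≤ 0. At least one holds in 10 × 15 + 36 × 7 = 402 of 7 × 15 × 15 = 1,575 combinations (25.5%).

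*Result for a child low at Weeks 8, 10 and 12 but not at Week 4.* On nominal dates, no adjacent pair qualifies. With every in-window day equally likely (an assumption), the literal rule counts this child in 25.5% of date combinations. Allowing the Week 8-12 pair when Week 10 is also low raises this to 94%.

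*Truncation.* SAP 2.1.4 and 2.3.1.1 end the OLDFI periods on the day before the first OLE injection for children who enter the OLE. Protocol 8.1.2 gives that injection at Week 12. Read literally, the pre-dose Week 12 sample falls just outside, although Table 3 lists Week 12 as an OLDFI time point. Only Week 8-10 then remains, at 10/105, and redefining the pair alone would not help.

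*Combined period.* Week 12 to Week 24 is 84 days (63 to 105 with windows of ±7 and ±14), so a child who enters the OLE and is low at both visits can be counted there.

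**The case against.** The other side has substantial points.

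- **A reader might infer that nobody watches Cohort 4 lipids after Week 8.** The documents do not say that. Regular DMC review runs through the dose-finding period, Protocol 6.4 includes Cohort 4, and the DMC receives unblinded lipids without a stated time limit. Further detail sits in a charter that is not part of these documents. The 8-week phrase looks like wording left from before Cohort 4 was added. What stands is narrower: the general passages state neither the low-LDL-C trigger nor the sponsor's action.
- **A reader might infer that Cohort 4 cannot meet the SAP rule.** It can. Week 4-8 always meets the spacing, some in-window dates do after Week 8, and Week 12-24 can in the combined period. The SAP also does not define *consecutive*, so a sustained-run reading is open. That ambiguity itself needs closing.
- **A reader might infer that the fall after the third injection is missed.** Week 10 is sampled (Protocol 10.1.2.6) and summarised by time point (SAP 2.4.4.2.4). It is the very-low-LDL-C rule that normally does not flag it. Nor is the third injection a higher dose: each child's planned dose is the same at Weeks 0, 4 and 8.
- **The SAP rule is descriptive.** The protocol trigger needs only one low value, and TEAEs are tabulated for the whole safety population regardless of subgroup. This limits the harm but does not make the subgroup correct.
- **No number of missed children can be given.** The documents contain no Cohort 4 response distribution. Protocol 4 reports mean changes of −7.7% in Cohort 3 and −46.1% in Cohort 2, and hopes for an effect closer to 50% in Cohort 4. A child with a baseline of 130 mg/dL needs a fall of more than (130 − 50)/130 = 61.5% to go below 50. Few children or several might qualify.

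**Conclusion.** The point holds in two limited parts.

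1. Protocol 6.1 assigns close monitoring and sponsor action on very low LDL-C for 8 weeks, while Cohort 4 is treated and masked for 12. On the wording, this covers two of its four post-baseline lipid samples. The clear gap is Week 10, plus Week 12 for children who do not enter the OLE. It is a gap in an explicit statement, not evidence that monitoring stops.
2. Read literally, the SAP rule normally leaves a child who is low at Weeks 8, 10 and 12 but not at Week 4 out of the OLDFI proportion, the time-to-first analysis and the TEAE subgroup. The nominal gaps of 14 days come straight from the plan. The 25.5% and 94% describe date combinations, not patients, and rest on strictly adjacent pairing, equally likely in-window days and inclusion of the Week 12 sample. Visits clustered near their target dates would make the literal rule count fewer.

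With about 10 children in Cohort 4, the absolute effect is at most a few children and may be none. The correction is still worth making because it is nearly free and concerns a safety subgroup.

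**What to change.** **Protocol.** Reconcile the 8-week wording in 6.1 with the 12-week Cohort 4 period, the DMC provisions in 6.1, 6.4 and 8.3.4, and the OLE-only scope of 10.6.3, so that it is clear which text governs the masked Week 10 and Week 12 results. What action should follow is for the sponsor and the DMC; none is proposed here.

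**SAP 2.1.4.7.** Define the endpoint as two values below the threshold at least 21 days apart with no intervening value at or above it. State that the pre-dose Week 12 sample of Cohort 4 children entering the OLE belongs to the OLDFI period for this endpoint. Both parts are needed, because the first does not help OLE entrants without the second. The time-to-first analysis and the TEAE subgroup in 2.4.5.1 then inherit the definition. A child low only at Weeks 8 and 10, or only at Weeks 10 and 12, would still normally not count, which is consistent with a rule that asks for persistence over 21 days.

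**Cost.** One clarification in the protocol and two sentences in the SAP, ideally before the second database lock. No new samples are needed and no threshold changes.
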